10.3 Planned Analyses

The analysis of **intervention-related outcomes** is primarily regarded descriptive. For **patient-related outcomes** parametrical and/or non-parametrical univariate statistics for pre-to post changes will be used.

10.3.1 Primary Analysis

Intervention-related outcomes: Absolute and relative frequency together with parameters of central tendency and spread will be derived for any devices used, duration of intervention per day, per session, per device. This applies analogously for training and feedback modes used and for self-perceived exertion rates. Adherence rates will be examined by using Chi-Square statistics.

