4.5 Primary Outcome

The primary outcome is to assess the feasibility of planned trainings. Every training and training day will be described in terms of

- devices used,
- duration of training,
- training mode (passive, active or resistive) and
- feedback given by the device.

The specific interest is the adherence of the patients:

- to planned trainings in terms of planned vs. actually performed training-days and training intensity.

- the subjectively perceived effort by the patients to perform the trainings will be recorded on a visual analogue scale (VAS).
- the subjectively perceived effectiveness will be recorded by using the “Patients Global Impression of Change” = PGICS)

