5 STUDY DESIGN AND COURSE OF STUDY

5.1 General Study Design and Justification of the Design

Since the aim of this feasibility study is the development and validation of a new treatment program and not yet, the investigation of effectiveness while controlled with a current state of the art intervention, no control group will be included. A longitudinal single group design has been chosen. Blinding of therapists and patients is accordingly not possible. Blinding of assessment cannot be guaranteed, due to logistical reasons and as assessments are either self-conducted or by attending therapists, who are trained in doing so.

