6.4 Criteria for Withdrawal/ Discontinuation of Participants

Patients not willing to adhere to the protocol will not be included. For included patients who, while having already attended some session but are not able to complete the six weeks program within the intensity planned, a tailored reduction of intensity in terms of days, hours per days and/or sessions per day is considered. A maximum training break of 7 days is foreseen

Patients who withdraw before the start of the study will be replaced.

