7 STUDY INTERVENTION

7.1 General Information

7.1.1 Study Intervention

- Series of tailored rehabilitative training with the use of new technology which provide feedback and allow for a targeted and intensive and dense training.
- With supervision based on patients preconditions and therapy device (e.g. patient/therapist ratio= 3/1).
- A training series lasts four weeks and comprises 3-5 training-days per week. Maximum training break of 7 days. Five sessions of training with duration of 45 min per session, and up to four hours each day are foreseen.
- The training can take place in an outpatient or inpatient setting.
- Training will be organized in individual one-to-one or group sessions.

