10 STATISTICAL METHODS

10.1 Hypothesis

Not applicable, as this study is a feasibility study. **Determination of Sample Size**

Twenty patients, five at each site are planned to be enrolled. A sample size calculation is not applicable for this feasibility study.

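### The Chi-Square planned for adherence has no two independent groups to compare, and its p-value follows the counting unit, the length of the plan and the degrees of freedom

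*Combined protocol and SAP*

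**What the plan says.** Section 4.5, repeated in 8.2.1, puts the adherence of patients at the centre of the primary outcome, namely adherence "to planned trainings in terms of planned vs. actually performed training-days and training intensity". Section 10.3.1 lists frequencies, central tendency and spread for devices, durations, training and feedback modes and perceived exertion. Adherence is not in that list. It has its own sentence: "Adherence rates will be examined by using Chi-Square statistics". No table, counting unit, reference rate or significance level is attached.

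The setting is a single group: "no control group will be included" (5.1). On a hypothesis, section 10.1 says "Not applicable, as this study is a feasibility study". Section 10.3 states that the analysis of intervention-related outcomes "is primarily regarded descriptive".

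The planned amount of training comes from 7.1.1: "A training series lasts four weeks and comprises 3-5 training-days per week", with five 45-minute sessions on a training day. Section 7.3 calls for an individual plan made in advance. Under 6.4 that plan can be cut back during the programme: "a tailored reduction of intensity in terms of days, hours per days and/or sessions per day is considered".

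**The concern.** A Chi-Square test needs either groups to compare or a reference rate to test against. The plan names neither. The one contrast to be found is planned against performed (4.5), and it does not suit the test. Performed training is a subset of planned training. If the reference is full delivery of the plan, the expected number of missed units is zero, and a proper two-cell goodness-of-fit statistic cannot be computed.

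If the analyst goes ahead with some version of the test, the p-value will mostly reflect choices that the protocol leaves open. At stake is the reporting of adherence itself: a reader planning a later trial needs to know how much of the plan 20 patients completed and how precisely that is known. No interval for adherence is planned.

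**Working it through.** **Inputs from the protocol.** 4 sites × 5 patients = 20 patients, which reproduces the stated sample size (10.1). Planned days per patient: 4 weeks × 3 to 5 = 12 to 20 (7.1.1), so 240 to 400 in total. At five sessions per day: 1,200 to 2,000 sessions in total.

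**Assumptions.** The protocol gives no adherence rate and no significance level. I use 80%, 90% and 95% adherence and a 5% level.

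**Step 1: the statistic.** Let P be the planned count (taken as expected) and d the shortfall. Performed is P(1 − d), so

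X² = (P(1 − d) − P)² / P = P·d².

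For a given d, the statistic is proportional to the number of units counted. Days become sessions by a factor of 5, and so does X².

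**Step 2: pooled count, 1 degree of freedom.**

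| Adherence | Unit | P | X² = P·d² | p |
|---|---|---|---|---|
| 90% | days, 3 per week | 240 | 240 × 0.01 = 2.4 | 0.12 |
| 90% | days, 5 per week | 400 | 400 × 0.01 = 4.0 | 0.046 |
| 90% | sessions, 3 days per week | 1,200 | 1,200 × 0.01 = 12.0 | 5e-4 |
| 90% | sessions, 5 days per week | 2,000 | 2,000 × 0.01 = 20.0 | 8e-6 |
| 95% | days, 5 per week | 400 | 400 × 0.0025 = 1.0 | 0.32 |
| 95% | sessions, 5 days per week | 2,000 | 2,000 × 0.0025 = 5.0 | 0.025 |
| 80% | days, 5 per week | 400 | 400 × 0.04 = 16.0 | 6e-5 |
| 80% | sessions, 5 days per week | 2,000 | 2,000 × 0.04 = 80.0 | 4e-19 |

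The 5% point on 1 degree of freedom is 3.84. A 10% shortfall therefore becomes significant once P exceeds 3.84/0.01 = 384 units. The protocol's own range of 240 to 400 days straddles that value, so the result can change even with days fixed as the unit.

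**Step 3: degrees of freedom.** Take one cell per patient instead of a pooled count. With 20 planned days each and every patient at 80%, X² = 20 × (4²/20) = 16, the same value as before. On 20 degrees of freedom p = 0.72 (0.66 on 19), against 6e-5 on 1.

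**Step 4: what counts as planned.** Suppose a plan of five days per week is cut to three after week 1 and every remaining day is kept. Performed days are 5 + 3 × 3 = 14. That is 14/20 = 70% of the first plan and 14/14 = 100% of the reduced one. Sections 8.3 and 8.3.3 add a plan made on each training day, a third possible denominator. Programme length matters too: 6.4 speaks of patients who "are not able to complete the six weeks program within the intensity planned", against four weeks in 7.1.1 and the synopsis. Going from four to six weeks at the same weekly frequency multiplies P, and hence X², by 6/4 = 1.5.

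**The case against.** The strongest reply is that the analysis is declared mainly descriptive, that no decision rule uses the test, and that 4.5 and 8.2.1 do supply a contrast and one unit, training days. All of this is true, and it limits the harm. It does not rescue the test. Nothing links those sections to the Chi-Square, training intensity has no stated unit, and Step 2 shows p crossing 0.05 within the planned range of days. A descriptive aim is an argument for an estimate with an interval.

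Two stronger readings are tempting.

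- A reader might infer that choosing days or sessions always decides significance. It does not. At 80% adherence on 1 degree of freedom both reject. In a 2×2 table of planned against performed, pooled days and sessions both reject at shortfalls of 5%, 10% and 20% (for 400 days at 90%, X² = 42.1). The size of the statistic always follows the unit; the verdict follows the unit together with the table, the degrees of freedom and the shortfall.
- A reader might infer that the test produces many false positives. With days pooled across patients, 80% adherence and an intraclass correlation of 0.1, simulated error is 16–26% against a fixed rate and 29–44% between four sites. Neither contrast is stated in the documents, and both the adherence rate and the correlation are assumed. These figures do not support the point.

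It is also fair to say that dropping the test and reporting descriptively would be enough, and that the interval proposed below is one reasonable choice among several.

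**Conclusion.** The point holds and is minor. Applied to the only contrast the documents suggest, the Chi-Square compares a quantity with part of itself. For the same 90% adherence, p runs from 0.12 to 8e-6 according to the unit and the number of planned days. At 80%, the same X² of 16 gives 6e-5 or 0.72 according to the degrees of freedom. The adherence rates and the 5% level are assumptions, but the relation X² = P·d² does not depend on them.

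The consequence is confined to an uninterpretable p-value and the absence of any statement of precision. A reader might infer that the feasibility conclusion is itself undermined. The documents do not support that, since no threshold or decision is tied to the test.

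**What to change.** Replace the adherence sentence in 10.3.1 with:

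> Adherence is computed for every enrolled patient, including drop-outs and patients excluded under 7.3 (see 10.4), as performed/planned training days, sessions and minutes. Planned means the individual plan made before training starts (7.3, 8.3.2), not the plan of the day (8.3, 8.3.3) and not a later reduced plan (6.4). All patient values are shown, with mean, median and range, overall and by site. The median is given with a distribution-free 95% confidence interval (6th to 15th ordered value if n = 20), which treats patients as independent and applies to these four clinics. No Chi-Square test is done.

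Drop-outs and exclusions are named because 7.3 excludes patients who do not fulfil the minimum programme, while 7.4 and 10.4 keep all patients in the analysis. Days, sessions and minutes measure the planned amount of training. Section 6.4 lists ways of reducing the programme and does not define intensity, so other device measures in the synopsis, such as repetitions, should be reported descriptively alongside.

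**Costs and limits.**
- No new data are needed: the individual plan lists days and sessions (7.3), and duration is recorded (4.5).
- Nominal coverage of the interval is 1 − 2 × P(Bin(20, 0.5) ≤ 5) = 95.9% for independent patients. It ignores clustering by site. If sites are treated as random draws (assumed: patient intraclass correlation 0.1, 80% adherence), simulated coverage is about 94% for 20 days and 87–88% for 100 sessions per patient at a site correlation of 0.05. At 0.1 it is 89–90% and 81–82%. Hence the restriction to these four clinics.
- A median can hide drop-outs, so the mean and all patient values must appear with it.
- Under 2.9 a change to the form of statistical analysis needs ethics committee approval, and three committees are involved (2.3).

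Two inconsistencies affect the planned denominator and must be reconciled: the four-week programme (synopsis, 7.1.1) against six weeks (6.4), and five training blocks per day as a minimum (synopsis) against five sessions (7.1.1).

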10.3.2 Secondary Analyses

For **patient related outcomes** pre-post analysis will be performed by parametrical or non-parametrical univariate tests. Subgroup analysis for upper and or lower extremity will be done.

For **Cost elements** and cost description analysis, descriptive analysis will be performed including costs for technology, staff and infrastructure. Efficiency gains and suitable reimbursement models will be calculated.

10.3.3 Interim Analyses

n.a.

10.3.4 Safety Analysis

n.a.

10.3.5 Deviation(s) from the Original Statistical Plan

n.a.

10.4 Handling of Missing Data and Drop-Outs

Primary analysis is according to intention to treat – and all patients will be included.

For secondary analysis, all participants with equal or less than seven days training break of the planned training will be included only.

Analysis of drop-outs will be carried out to find reasons or barriers (CRF) that might explain why sticking to the treatment plan was not possible, whether related or unrelated to the intervention.

11 ELIGIBILITY OF THE PROJECT SITE(S)

Four rehabilitation centres located across the German speaking area of Switzerland will participate in this project.

Klinik Lengg, Zurich

The Klinik Lengg has a workload of 250-stroke patients a year. All patients fulfilling the inclusion criteria will be asked for participation.

Reha Rheinfelden

The Reha Rheinfelden has a workload of approximately 400 ischaemic and haemorrhagic stroke patients as in-and outpatients a year, which will be recruited via direct contact and flyer distributed in-house.

Kliniken Valens

Kliniken Valens treated approximately 460 ischaemic and 150 haemorrhagic stroke inpatients a year, who will be approached by a research assistant to check their eligibility while entering the clinical site for inpatient rehabilitation.

Rehaklinik Zihlschlacht

The Rehaklinik Zihlschlacht has a yearly workload of approximately 300 stroke patients; some of them will be treated after discharge in the clinic's outpatient setting. Study personnel will approach patients regarded eligible for further evaluation.

Each site aims to include five patients leading to 20 patients in total. Study sites are entering the study consecutively and according to their personnel capacity. **Each site aims to include five patients** leading to 20 patients in total. Study sites are entering the study consecutively and according to their personnel capacity.

12 DATA QUALITY ASSURANCE AND CONTROL

The Sponsor-Investigator will provide all study sites with case report forms and written instructions. All study sites ensure that the trial is conducted and data are generated, documented (record), and reported in compliance with the protocol, GCP, and applicable regulatory requirement(s).

Monitoring and Audits will be conducted during the course of the study for quality assurance purposes.

12.1 DATA HANDLING AND RECORD KEEPING

The study will strictly follow the protocol. If any changes become necessary, they must be laid down in an amendment to the protocol. All amendments of the protocol must be signed by the Sponsor-Investigator and if essential submitted to CEC.

12.1.1 Case Report Forms

The investigators will use *paper* case report forms (CRF), one for each enrolled study participant, to be filled in with all relevant data pertaining to the participant during the study. All participants who either entered the study or were considered not eligible or were eligible but not enrolled into the study additionally have to be documented on a screening log. The investigator will document the participation of each study participant on the Enrolment Log.

CRFs will be kept current to reflect participant status at each phase during the course of study. Participants must not to be identified in the CRF by name. Appropriate coded identification (e.g. **SRTI_ClinicCode_Number**) must be used.

It must be assured that any authorized person, who may perform data entries and changes in the CRF, can be identified. A list with signatures and initials of all authorized persons will be filed in the study site file and the trial master file, respectively.

The investigators assure to perform a complete and accurate documentation of the participant data in the CRF. All data entered into the CRF from *original questionnaires and assessment sheets* will also be available in the individual participant file either as print-outs or as notes taken by either the investigator or another responsible person assigned by the investigator.

Essential documents will be retained for at least 10 years after the regular end or a premature termination of the respective study (KlinV Art. 45).

Any patient files and source data will be archived for the 10 years at each study site.

12.1.2 Specification of Source Documents

The following documents are considered source data, including but not limited to:

- SAE worksheets
- Case report forms

Source data must be available at the site to document the existence of the study participants and substantiate the integrity of study data collected. Source data must include the original documents relating to the study, as well as the medical treatment and medical history of the participant.

The following information (at least but not limited to) should be included in the source documents

- Demographic data (age, sex)
- Inclusion and Exclusion Criteria details
- Participation in study and signed and dated Informed Consent Forms
- Visit dates
- SAEs (related) and concomitant medication
- Reason for premature discontinuation

12.1.3 Record Keeping / Archiving

All study data will be archived for a minimum of 10 years after study termination or premature termination of the clinical trial at each study site in a lockable and fireproof place. Informed consents and CRFs will be archived in separate places. Original study documents including any documents with personal information will be kept at the study site. There will be kept in fireproofed locker, accessible only by Study personnel. Copies of CRFs, including the clinic code will be transferred to the Sponsor investigator site and will be kept on a secure data pool only accessible by involved study personnel. The data pool will be closed after the end of the study and will by then only be accessible according to the separation of duties (SOD) principle.

12.2 Data Management

Copies of the CRF will be transferred by each site investigator and uploaded on a security pool at the sponsor investigators site. Original data will be kept at the clinical site in a lockable and fireproof place, the informed consent will be separated from other documents. Only study personnel involved in the clinical trial will have access to that security pool. No personnel data will be transferred but kept at each study site and separated from the CRF. Data from CRFs will be entered to electronic spreadsheets using double data entry and saved as raw file. During further data processing and analysis, edited files will be renamed with actual dates and acronyms of the responsible person. Original files (paper or electronic) will not be changed

12.3 Routine Monitoring

Monitoring visits at the investigator's site prior to the start and during the course of the study will help to follow up the progress of the clinical study, to assure utmost accuracy of the data and to detect possible errors at an early time point. The Sponsor-Investigator organizes professional independent monitoring for the study.

All original data including all patient files, progress notes and copies of laboratory and medical test results must be available for monitoring. The monitor will review all or a part of the [CRF](#) and written informed consents. The accuracy of the data will be verified by reviewing the above referenced documents.

12.4 Audits and Inspections

A quality assurance audit/inspection of this study may be conducted by the CEC. The quality assurance auditor/inspector will have access to all medical records, the investigator's study related files and correspondence, and the informed consent documentation that is relevant to this clinical study.

The investigator will allow the persons being responsible for the audit or the inspection to have access to the source data/documents and to answer any questions arising. All involved parties will keep the patient data strictly confidential.

12.5 Confidentiality, Data Protection

Direct access to source documents will be permitted for purposes of monitoring, audits and inspections to the authorities of the responsible ethical committees.

13 PUBLICATION AND DISSEMINATION POLICY

After the statistical analysis of this trial, the sponsor will make every endeavor to publish the data in a medical journal.

14 FUNDING AND SUPPORT

14.1 Funding

This study receives funding from an anonymous Swiss Foundation.

14.2 Other Support

NA

15 INSURANCE

Insurance is covered by "Versicherung für klinische Versuche und nichtklinische Versuche" by Zürich Versicherungs-Gesellschaft AG (Policy no.: 14.237.322).

Any damage developed in relation to study participation is covered by this insurance. So as not to forfeit their insurance cover, the participants themselves must strictly follow the instructions of the study personnel. Participants must not be involved in any other medical treatment without permission of the principal investigator (emergency excluded). Medical emergency treatment must be reported immediately to the investigator. The investigator must also be informed instantly, in the event of health problems or other damages during or after the course of study treatment.

The investigator will allow delegates of the insurance company to have access to the source data/documents as necessary to clarify a case of damage related to study participation. All involved parties will keep the patient data strictly confidential. A copy of the insurance certificate will be placed in the Investigator's Site File.

